Protocol Cover Page

Title: Familial Hyperlipidemia Family Registry

NCT Number: 05814419

Version Date: 02MAR2023

Protocol: Familial Hyperlipidemia Family Registry

Principal Investigator(s): [name]

Main Study Site: [name]

Protocol Version Date: March 2, 2023

Protocol Version Number: 2

IRB # 22-1979

I. Hypothesis and Specific Aims

If a child from the Healthy Hearts and Minds education and screening program is found to have a genetic marker for familial hyperlipidemia, immediate family members are offered genetic testing at no charge to identify those at high risk for cardiovascular disorders and those who carry the genetic markers. If identified early, the risk for cardiovascular disease can be greatly modified by early and proper treatment.

The aim of the study is to gauge the impact of large-scale surveillance testing to identify those with the disorder and improve clinical care. This impact is both in disease prevention and in lessening the cost of long-term care from premature cardiovascular disease.

II. Background and Rationale

UCHealth Healthy Hearts and Minds education and screening program routinely screens 5th, 7th, and 10th graders for lipid and blood pressure status on an annual basis. Children with cholesterol levels greater than 200 mg/dl have been invited to participate in a Familial Hyperlipidemia protocol to identify individuals/families with genetic markers for lipid disorders.

Familial hyperlipidemia has four primary genetic types – LDL, LDLR, PCSK9 and Apo lipoprotein B. Individuals with familial hyperlipidemia, either heterozygote or homozygote, are at increased risk for cardiovascular events starting early in life.

Approximately 1 in 300-500 people have the heterozygote genetic profile, where as a homozygous genetic profile is very rare at 1 per one million. The cardiovascular risk for heterozygotes is increased 5–10 times over the normal population and the process begins much earlier in life. If these individuals are identified early, they have a greater than 80% chance to decrease their long-term risk of cardiovascular disease and have risks similar to the normal population.

Recent evidence show that a small percentage of relatives pursue follow-up testing despite having a 50% risk of having the same variant. Reasons for not pursuing the testing include lack of knowledge about the potential disease risk, family communication barriers, lack of access to genetics services, and cost of testing.

Healthy Hearts and Minds partnered with Invitae to utilize their family variant testing. Invitae offers a no charge genetic test to biological family members for the variant that the biological related child tested positive for. Invitae provides no cost testing as a

commitment to lowering barriers to genetic testing and to increase access to genetic information that can help family members make informed health decisions.

III. Research Methods

a. Outcome measures: Children from the Healthy Hearts and Minds education and screening program who have been identified as having elevated cholesterol >200 mg/dl will be invited to be tested for genetic markers of Familial Hyperlipidemia. If positive for LDL, LDLR, PCSK9 or Apo lipoprotein B, immediate family members will be offered free lipid profiles, free genetic testing and referral to appropriate consultation for treatment of lipid disorders in adults or children. Family trees will be developed to ensure contacts are complete so each individual is allowed access to the lipid and genetic testing. The registry will catalogue family trees of the affected families to allow better identification of those who have the variant.

General health and medical information will be collected. A health questionnaire relating to cardiovascular disease and cardiovascular risk factors will be filled out for each biological family member (Appendix A). This will include questions about heart disease, high blood pressure, elevated cholesterol, and health habits. REDCap will be utilized to administer questionnaires. These forms will be collected, uploaded and stored in secure databases that only the research team will have access via their secure login and password. All data will be de-identified when presented outside of study.

b. Description of population to be enrolled:

Inclusion criteria: Any biological relative of the child who had a positive result for familial hyperlipidemia that participated in the “School-based Education and Screening Program with Lipid Screening as a Means to Identify Familial Hyperlipidemia study” (IRB 20-6010) will be invited to enroll. Children from 6 months old to adults of any age may enroll.

As the genetic test will be provided by Invitae for no cost to all biological family members of the identified child as part of the family variant testing program, the number of genetic tests performed is not restricted by budgetary constraints. In addition, the limitation for numbers to enroll is based on the number of children from the familial hyperlipidemia study that are discovered to have a positive result for the gene and the number of biological relatives that request to receive a free genetic test. It is estimated that 10-20% (approximately 10-20 children) who enroll in the IRB 20-6010 study will be positive for familial hyperlipidemia and therefore no more than 5,000 biological relatives will enroll in this study.

Exclusion criteria: A participant may not enroll in the study if they are not biologically related to a child who was informed they have a positive result for familial hyperlipidemia from the IRB 20-6010 research study.

c. Study Design and Research Methods:

Children from the Healthy Hearts and Minds education and screening program identified as having elevated cholesterol >200 mg/dl will be tested for genetic markers of Familial Hyperlipidemia as part of the IRB 20-6010 study, which began in August 2022. Only the biological family members of a child with a positive test will be included in the study.

It is the responsibility of that child's parent or guardian to contact extended biological family members and inform them of their ability to receive their own family genetic testing kit. A flyer (Appendix B) will be provided which they can send to their immediate family members that will inform them on how to receive the free genetic test.

The family members have 150 days from the child's positive result to receive a free genetic test from Invitae. Once they contact the Healthy Hearts and Minds Research team, they will schedule their study visit to perform the genetic test and lipid panel. If the biological family member has already completed a genetic test or lipid panel, they can provide us with the testing results.

If a participant already performed the genetic test at any time point, they can provide their results for LDL, LDLR, PCSK9 and Apo lipoprotein B.

A translator will be made available and all materials will be translated by a certified medical translator if needed.

Study visits: Visits will occur at the Healthy Hearts and Minds office located at [name]. A visit will last approximately 30-45 minutes. If the participant chooses, they may opt have the study kit mailed to them in order to perform the buccal swab at their home.

Study duration: Enrollment for the study will continue until 150 days after the final child that enrolls in IRB 20-6010 has their familial hyperlipidemia test resulted. Anticipated enrollment end date is July 30, 2025.

Study visit one:

Consent process

The consent form will be reviewed and signed by the adult participating. If a child is participating, the child will be provided an assent to read over and agree to participate as well. Everyone will be able to ask questions regarding the study. The signature of only one parent or guardian will be required for a child to participate. The Guidance on the Genetic Information Nondiscrimination Act (GINA) will be

reviewed. A certified genetic counselor, provided by Invitae, will be available to answer questions if needed. The use of e-consent will be used for this study via REDCap. The consent conversation with the potential participant will be in person or via Microsoft Teams. An exact copy of the informed consent will be loaded into REDCap and used in place of the paper form. The delegated staff member conducting the informed consent will do so in the same manner as providing informed consent as they would a paper copy. The delegated staff member conducting the informed consent and the participant will electronically sign the informed consent in REDCap. A copy of the signed e-consent will be emailed/mailed after based on their preference. The consent conversation will not change, the e-consent will be on a tablet. A paper consent form will be available if the participant's requests.

Sample collection

Post consent, the health history questionnaire will be obtained. In addition, genetic testing for familial hyperlipidemia and a lipid panel will be performed as outlined below:

- **Invitae genetic testing kit:** A buccal cheek swab will be utilized to collect the sample. The participant will be required to not have had any food or drink 30 minutes before the cheek swab. If the participant has previously performed the test for LDL, LDLR, PCSK9 and Apo lipoprotein B, they can opt out of the buccal swab and provide a copy of their familial hyperlipidemia results.
- **A lipid panel:** A finger stick utilizing the CardioChek Plus analyzer will be used to collect the sample. The test utilizes capillary blood and will provide results for HDL (high density lipoprotein), LDL (low density lipoprotein), and triglycerides. If the participant has already performed a lipid panel in the previous year, then they can opt out of the finger stick and provide a copy of their recent lipid panel results.

Results will be provided to the family when processed and available in approximately 4-12 weeks. The results will also be scanned and entered into the child's electronic medical records (EMR). A copy of the genetic test results can be forwarded to the child's primary care provider if requested. All participants will be offered access to clinical care for their lipid abnormalities, either through Cardiology or Pediatrics. Cost of care will be through their insurance carrier.

D. Description, Risks, and Justification of Procedures and Collection Tools.

There are no significant risks from this study. For the genetic test, there may be a slight discomfort with the cheek swab. Staff will utilize CardioChek devices and collect blood with a small finger stick blood sampling method. Risks for this capillary blood sampling are minimal, but include potential discomfort, bruising and infection.

Proper blood safety standards will be followed to minimize any potential participant and screener risk.

E. Potential Scientific Problems. There are no factors that could threaten our ability to obtain meaningful generalizable knowledge other than hesitation by a family to bring their child in to participate in a study during a pandemic may confound our sample.

F. Data Analysis Plan. Data from the family members will be tabulated and analyzed to create a family tree using R Studio and excel. Percent of family members tested who have familial hyperlipidemia will be calculated as well as estimated health care cost saving with early identification of families with the disorder.

G. Summarize Knowledge to be Gained:

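### Offer and flyer wording is narrower than the eligibility rule, and Section F pools relatives of every degree into one percent positive

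*Combined protocol and SAP*

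**What the plan says.** **Who may enroll.** Section III.b (inclusion) invites "Any biological relative of the child who had a positive result for familial hyperlipidemia", given that the child took part in the linked screening study. The exclusion criterion is the mirror image: "A participant may not enroll in the study if they are not biologically related to a child" with a positive result from that study. The same section says the free test is open to all biological family members and caps enrollment at 5,000 biological relatives, from an expected 10-20 positive children.

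**Who is offered testing.** Section I says "immediate family members are offered genetic testing at no charge". Section III.a says "immediate family members will be offered free lipid profiles, free genetic testing and referral" for treatment.

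**Who is told.** Section III.c makes it the responsibility of the child's "parent or guardian to contact extended biological family members". The next sentence provides a flyer (Appendix B) "which they can send to their immediate family members". Neither 'immediate' nor 'extended' is defined.

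**What is reported.** Section F calculates one percentage, those with familial hyperlipidemia among family members tested, and plans no breakdown by relationship. Appendix A, item 2, records each participant's relationship to the identified child and whether it is on the paternal or maternal side.

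**The concern.** There are two separate problems.

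1. **Outreach.** The family learns of the study through the parent or guardian, and the flyer is the one written outreach item the protocol names. If it goes only to immediate family, eligible grandparents, aunts, uncles and cousins may never hear of a free test that is available for 150 days after the child's result. Section II itself lists lack of knowledge and poor family communication among the reasons relatives go untested.

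2. **Interpretation.** The chance of carrying the child's variant falls with distance of relationship. A pooled percentage therefore reflects who came forward as well as how the variant is transmitted. A reader shown a pooled 25%, for example, could not tell whether mostly distant relatives had been tested or close relatives had shown fewer carriers than expected. Section F also plans a cost-saving estimate with no stated method. Any version built on the number of relatives identified would need the same breakdown to be interpretable.

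**Working it through.** **Step 1: the wording side by side.**

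| Place | Scope |
|---|---|
| I, hypothesis | immediate family |
| III.a, offer of tests | immediate family |
| III.a, health questionnaire | each biological family member |
| III.b, inclusion, exclusion and free test | any biological relative |
| III.c, parent's or guardian's duty | extended family |
| III.c, flyer | immediate family |

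The three eligibility statements agree with one another. The narrower term occurs in three places, all of them offer or outreach text.

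**Step 2: the plan's own figures (III.b).**
- Index children: 10/0.10 = 100 and 20/0.20 = 100. The percentage and the count agree, on about 100 children enrolled in the linked study.
- Ceiling: 5,000/20 = 250 and 5,000/10 = 500 relatives per positive child. The protocol gives no number of relatives per child, so 5,000 cannot be reproduced. As an upper bound it fits only the broad reading.
- For contrast, assume 3-6 immediate relatives per child (not a document figure). Immediate family alone would be 10 × 3 = 30 to 20 × 6 = 120 people, or 30/5,000 = 0.6% to 120/5,000 = 2.4% of the ceiling.

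**Step 3: the pooled percentage.** Section II gives relatives a 50% risk without naming a degree. I take this as the first-degree figure and assume one carrier parent, dominant inheritance, halving per degree (25% second, 12.5% third), and that those tested within a degree are typical of it. Then

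expected percent positive = w1 × 50 + w2 × 25 + w3 × 12.5,

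where w1, w2 and w3 are the shares of those tested in each degree.

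| Mix (1st/2nd/3rd) | Sum | Result |
|---|---|---|
| 60/30/10 | 30 + 7.5 + 1.25 | 38.8% |
| 30/40/30 | 15 + 10 + 3.75 | 28.8% |
| 10/30/60 | 5 + 7.5 + 7.5 | 20.0% |

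The mixes are illustrative.

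**Step 4: does the wording cause this spread?** Suppose every sentence read 'any biological relative'. The denominator in Section F would still be whoever was tested, the shares would still be unknown in advance, and the formula in Step 3 would give the same results. The spread comes from pooling.

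**The case against.** The strongest case on the other side has four parts.

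- **Eligibility is settled.** A reader might infer that the protocol has three rival target populations. It does not. Inclusion, exclusion and free-test text all say any biological relative, and the stated aim of large-scale surveillance testing fits that. This stands: the wording can affect who hears of the study, but not who qualifies.
- **The flyer sentence may be consistent.** 'Their' could refer to the parent or guardian, whose own parents and siblings are the child's extended family. The sentence is also permissive, and Appendix B is not in the text available for review, so whom the flyer addresses cannot be checked. This reading is possible, though not the most natural one, and it does nothing for Sections I and III.a.
- **The flyer is not the only route.** The parent or guardian must inform extended relatives in any case, family trees are drawn up so that contacts are complete, and Appendix A asks for other associated family members. This stands, and it limits the likely loss.
- **The breakdown can be done anyway.** Section F is descriptive, names no main result and plans no comparison with 50%. The data for a tabulation by degree will exist. All true, but the plan does not commit to one, and the pooled figure is hard to interpret without it.

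**Conclusion.** The point holds in two independent parts.

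**Wording.** The offer text in Sections I and III.a, and the flyer sentence in III.c as most naturally read, are narrower than eligibility. The flyer sentence also sits awkwardly beside the instruction to contact extended family. This may reduce outreach. The documents do not allow the loss to be sized, because they give neither the number of relatives per family nor the flyer text.

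**Analysis.** The single percentage in Section F depends on the mix of relatives tested. Under the assumptions in Step 3, three plausible mixes move it from 38.8% to 20.0% with no change in the underlying genetics.

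A reader might go further and say that the inconsistent wording makes the result anything from 12.5% to 50%. The documents do not support that. Those ends require a registry made up only of third-degree or only of first-degree relatives, and the dependence on mix would remain after the wording was corrected. Nor does the result turn on which sentence staff follow, since Section III.c assigns outreach to the parent or guardian.

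Neither part invalidates enrollment. Both are worth correcting because the changes are small and the data are already planned.

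**What to change.** 1. **Wording.** Replace 'immediate family members' with 'biological relatives of any degree' in the three places it occurs: Section I, Section III.a and the flyer sentence in Section III.c. Make the flyer in Appendix B match. The eligibility text needs no change.

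2. **Section F.** Report percent positive, with numerator and denominator, separately for first-degree, second-degree and more distant relatives, using the relationship and paternal/maternal fields in Appendix A. Show the pooled figure beside them.

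**Cost.** A few words in three sentences, a check of the flyer and one added line in Section F, with no new data. The downside is smaller denominators per group. If the first-degree group were 30-120 people (the assumed 3-6 per child from Step 2, all tested), the 95% half-width at 50% would be 1.96 × √(0.25/30) = 17.9 percentage points down to 1.96 × √(0.25/120) = 8.9 points, ignoring clustering within families. Keeping the pooled figure in the table means nothing now planned is lost.

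### Section F reports one positivity percentage and one early-identification saving without separating relatives already known before the child's result, so neither figure isolates what the testing newly found

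*Combined protocol and SAP*

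**What the plan says.** Section III.c, under Study Design and Research Methods, allows earlier results in general terms: "If the biological family member has already completed a genetic test or lipid panel, they can provide us with the testing results". It then removes any time limit for the genetic test: "If a participant already performed the genetic test at any time point, they can provide their results". Under Sample collection, a person with such a result may "opt out of the buccal swab and provide a copy of their familial hyperlipidemia results".

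The 150-day limit in Section III.c applies to obtaining the free test, not to results supplied from elsewhere. Section III.b has one exclusion: a person "may not enroll in the study if they are not biologically related to a child who was informed they have a positive result". Prior knowledge of the disorder is not a bar.

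Section F gives the whole analysis. "Percent of family members tested who have familial hyperlipidemia will be calculated", together with "estimated health care cost saving with early identification of families with the disorder". It gives no definition of *tested*, no cut-off at the child's result, no separate tabulation and no costing method.

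Section I states the aim, and Section G the knowledge to be gained, as the impact of large-scale surveillance testing in identifying people with the disorder. Section III.a adds a second purpose, the cataloguing of family trees.

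**The concern.** A relative whose condition was known before the child tested positive was not found by this programme. Such a person belongs in the family tree, but not in a figure that will be read as what the testing achieved. Section F leaves room for that reading because it has one percentage and one saving and says nothing about prior knowledge.

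There are two ways in. A relative may supply an earlier positive genetic result in place of the swab. A relative with an earlier clinical diagnosis may be genotyped for the first time in the study and appear as a new positive. Splitting by the source of the genetic result would catch the first and miss the second.

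What is at stake is interpretation. A reader of the final report could not tell how many of the affected relatives were new, or how much of the saving came from earlier identification.

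**Working it through.** The plan states no target, precision or expected percentage for this outcome, so there is no figure to reproduce. The check is a comparison of passages, followed by a short illustration.

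**Passages side by side**

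1. Entry: any biological relative may enrol (Section III.b), with an earlier genetic result of any age (Section III.c). Known affected relatives can be in the data.
2. Analysis: Section F neither removes nor flags them, and defines neither *tested* nor early identification.
3. Data: opt-outs hand over a copy of their result, so its source can be recovered, and its timing too if the copy is dated (assumption). Appendix A has open items on risk factors and cardiovascular disease, but does not ask whether the disorder was known before the child's result. An earlier clinical diagnosis may therefore be impossible to reconstruct.

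**Illustration for earlier genetic results**

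Inputs:
- *s*, the share of relatives with a genetic result who supply an earlier one: not in the documents; assumed 5%, 10% or 20%.
- *p*, positivity among newly tested relatives: 50%, the risk given in Section II. 25% is an assumed alternative.
- *q*, positivity among those with earlier results: not in the documents; the full range from 0 to 100%.

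Pooled percentage = (1 − s)p + sq. Shift from the new-only percentage = s(q − p).

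| p | s | q = 0 | q = p | q = 100% |
|---|---|---|---|---|
| 50% | 5% | 47.5% | 50% | 52.5% |
| 50% | 10% | 0.9 × 50% = 45% | 45% + 5% = 50% | 45% + 10% = 55% |
| 50% | 20% | 40% | 50% | 60% |
| 25% | 10% | 22.5% | 25% | 32.5% |

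The shift can go either way and is zero when q = p. An unmoved percentage does not remove the problem. With p = q = 50% and s = 10%, per 100 relatives there are 45 new positives and 5 already known, so 5/50 = 10% of the positives were not found by the programme. At q = 100% the share is 10/55 = 18%. This second quantity matters only if a count of positives is reported or used to build the saving.

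The illustration does not cover relatives diagnosed clinically but first genotyped in the study. The documents give no basis for a number there.

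**The case against.** The case for leaving the plan alone has real substance.

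- **Size.** Every value of *s* and *q* is assumed, and the ends of the ranges are extremes. Section II says only a small share of relatives pursue follow-up testing, and Section III.b ties enrolment to relatives asking for the free test. Both suggest that few will bring earlier results, though neither shows it. This stands and limits the weight of the point.
- **Wording.** *Tested* could mean tested within the study, and early identification could be read as leaving out people already known. This also stands. A reader might infer that the plan intends to credit known carriers to the programme. The documents do not say so; they leave it open.
- **Direction.** A reader might infer that the percentage will be inflated. The arithmetic does not support that, since it falls if those with earlier results are mostly negative.
- **Overcount.** A reader might infer that the plan overstates a number of carriers found. Section F plans a percentage and a saving, not such a count, and gives no costing method.
- **The lipid limit.** A reader might take the one-year limit on lipid panels as a sign that the open limit on genetic results is an oversight. It is not: lipid values change and an inherited variant does not.
- **Legitimate registry quantity.** Positivity among all relatives with a result is worth reporting, and known carriers belong in the family tree. This stands, so the overall percentage should be kept.

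What survives is narrower. The stated aim concerns identification by testing, and the plan has neither a rule nor a specific question that separates new identification from prior knowledge.

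**Conclusion.** The point holds as a minor one. As written, relatives known to be affected before the child's result can enter both the percentage and the early-identification saving, and neither figure then measures what Sections I and G set out to learn.

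The effect on the percentage has unknown size and direction. The 45% to 55% range rests on an assumed 10% with earlier results, the 50% risk from Section II for new relatives, and no restriction on positivity among the rest. If no enrolled relative was previously tested or known to be affected, nothing changes. The effect on the saving cannot be sized, because no costing method is given. Nothing here bears on participant safety or on the value of the family trees.

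**What to change.** **At enrolment**, add two REDCap fields:
- date of first genetic test for the disorder;
- whether familial hyperlipidemia, clinical or genetic, was known before the first positive result in a child of that family (yes/no).

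Using the first positive child in the family fixes the reference date when two related children test positive.

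**In Section F**, state that the percentage will be reported:
1. for all relatives with a genetic result, whatever its source or date;
2. separately for relatives who, before that reference date, were neither known to be affected nor genetically tested.

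Keep everyone in the family tree. Base statements about newly identified carriers, and the early-identification saving, on the second group only. One rule then serves both, and a relative diagnosed clinically years ago but genotyped later is not credited as new. A test done elsewhere after the reference date still counts for a relative not already known to be affected, which is fair because the programme may have prompted it.

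**Cost:** two more questions and a few lines of text. The child's result date is already needed for the 150-day window. The downsides are a smaller denominator for the impact figure and possibly a less favourable headline.

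### The planned percent positive among tested relatives cannot show how many carriers were reached, and Section E's denial of other threats conflicts with how relatives are recruited

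*Combined protocol and SAP*

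**What the plan says.** **Aim.** Section I states: "The aim of the study is to gauge the impact of large-scale surveillance testing to identify those with the disorder", and to improve care. It then describes impact as prevention and lower long-term cost.

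**Planned analysis.** Section F plans a tabulation and family tree, an estimated cost saving, and this proportion: "Percent of family members tested who have familial hyperlipidemia will be calculated". No section plans a proportion of eligible or informed relatives who were tested, or a split by degree of relationship.

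**Earlier results.** Section III.c accepts genetic results that a relative already has, from any date. For such a relative, "they can opt out of the buccal swab and provide a copy of their familial hyperlipidemia results". Section F does not say whether these relatives count as tested.

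**Source for a denominator.** Section III.a says: "Family trees will be developed to ensure contacts are complete so each individual is allowed access to the lipid and genetic testing". Item 2 of the questionnaire in Appendix A records the respondent's relationship and side of the family.

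**Who enters.** Section III.b ties enrollment partly to the "number of biological relatives that request to receive a free genetic test". Section III.c leaves it to the index child's parent or guardian to tell extended relatives.

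**What is known about uptake.** Section II says that a "small percentage of relatives pursue follow-up testing despite having a 50% risk of having the same variant". It says that the reasons "include lack of knowledge about the potential disease risk, family communication barriers", as well as access and cost.

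**Threats.** Section E states: "There are no factors that could threaten our ability to obtain meaningful generalizable knowledge other than hesitation by a family", and the hesitation it means is about bringing a child to a study during a pandemic.

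**The concern.** The Background gives low uptake among relatives as the obstacle, and free testing is offered to lower it. The analysis then conditions on having been tested, which removes uptake from view. A program that reached nearly all relatives and one that reached a few could report the same percentage.

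The percentage also depends on things the plan does not tabulate: how close the tested relatives are to the index child, whether carriers are more or less likely to come forward, and whether some positives were known before the program began. A reader would see one pooled figure and, beside it, a statement that nothing but pandemic hesitation limits its generalizability. What is at stake is whether the registry can say how many carriers it newly found, and out of how many it could have found.

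**Working it through.** **Inputs.** The protocol gives no count of eligible, informed or tested relatives, so there is no stated figure to reproduce. Two inputs come from the documents: the 50% risk (Section II) and 10-20 positive index children (Section III.b). Everything else below is assumed for illustration: relatives per child, 20 tested with 10 positive, a 25% risk in second-degree relatives, uptake ratios and numbers already known.

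**1. The percentage does not move with uptake.** With risk p, uptake uc in carriers and un in non-carriers, percent positive among tested = p·uc / (p·uc + (1 − p)·un). At p = 0.5:
- uc = un = 0.1: 0.05/0.10 = 50%
- uc = un = 0.3: 0.15/0.30 = 50%
- uc = un = 0.9: 0.45/0.90 = 50%

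The share of carriers found is 10%, 30% and 90%.

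**2. The same counts fit very different reach.** Take 20 tested and 10 positive. Eligible = index children × relatives per child; uptake = 20/eligible; expected untested carriers = 0.5 × (eligible − 20).

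| Index children | Relatives each | Eligible | Uptake | Untested carriers |
|---|---|---|---|---|
| 10 | 3 | 30 | 67% | 5 |
| 10 | 5 | 50 | 40% | 15 |
| 10 | 10 | 100 | 20% | 40 |
| 20 | 3 | 60 | 33% | 20 |
| 20 | 5 | 100 | 20% | 40 |
| 20 | 10 | 200 | 10% | 90 |

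If the untested relatives carry at 25% rather than 50%, the last column halves.

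**3. Mix of relatives.** With a fraction f first-degree (50%) and the rest second-degree (25%), the percentage is 0.5f + 0.25(1 − f). It is 50% at f = 1, 37.5% at f = 0.5 and 25% at f = 0.

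**4. Self-selection.** With uptake ratio r = uc/un, the percentage is p·r/(p·r + 1 − p).
- p = 0.5: r = 0.5 gives 0.25/0.75 = 33%; r = 2 gives 1/1.5 = 67%.
- p = 0.25: r = 0.5 gives 0.125/0.875 = 14%; r = 2 gives 0.5/1.25 = 40%.

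**5. Earlier results.** Suppose k of the 10 positives were known before the index child's result and no other earlier result is among the 20. The pooled figure stays 10/20 = 50%. New carriers are 10 − k, and positivity among new tests is (10 − k)/(20 − k). For k = 0, 2, 5 this is 10/20 = 50%, 8/18 = 44% and 5/15 = 33%.

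**6. Families with nobody enrolled.** If uptake were computed only in families with a tested relative, a true 10% with n relatives deciding independently would read 0.1/(1 − 0.9^n). That is 37%, 24% and 15% for n = 3, 5, 10. If instead 20% of families are informed and half of their relatives test, it reads 0.1/(0.2 × (1 − 0.5^n)) = 57%, 52% and 50%. An uptake figure must therefore say which families it covers.

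**7. Precision.** Treating relatives as independent, the SD of a 50% proportion is √(0.25/m): 22 points at m = 5, 16 at 10 and 11 at 20. With 10-20 families, descriptive counts are the right form.

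**8. Section E against Sections II and III.** Section II says that few relatives pursue testing and names communication within families as a barrier. Section III routes information to extended relatives through the parent or guardian and admits those who ask. Both are forms of selection into the tested group. Section E's one exception, about bringing a child in during a pandemic, covers neither an adult relative's choice nor whom the parent tells.

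**The case against.** The strongest reply is that uptake is not a stated outcome. Section I describes impact as prevention and cost, the registry's job is to catalogue family trees, and Section F plans the tree. The percentage names its own denominator, so nothing in it is false. This stands in part: the planned percentage is valid for what it describes, and the missing uptake measure does not invalidate it. But the aim names identification in its first clause, and both prevention and cost depend on carriers being found. The aim is therefore partly answered, not unanswered.

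It is also fair that most figures above are assumed. They show what the planned output cannot distinguish; they are not evidence that bias occurs.

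Some stronger readings are tempting but not supported:
- *The percentage will be too high.* The documents give no direction for self-selection.
- *Pooling earlier results will overstate the cost saving.* Section F gives no costing method and does not say that outside results would be credited to the program, so this cannot be determined.
- *The questionnaire cannot list untested relatives because item 9 has four lines.* It is administered in REDCap, where printed lines need not be a limit. The printed form also lacks the health-habits questions that Section III.a promises, so it may not be the whole instrument.
- *The 5,000 ceiling is the denominator.* It implies 5,000/20 = 250 to 5,000/10 = 500 relatives per positive child. It is an upper limit on enrollment, not a count of eligible relatives.

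**Conclusion.** The point holds in this form. Section F's only identification result is the percent positive among relatives tested. It has no uptake measure, no breakdown by degree and no separation of results that predate the index child's. That percentage has the same expectation at any uptake unrelated to carrier status and relationship. It also shifts with the mix of relatives (50% to 25% in the illustration) and with self-selection (33% to 67% around a true 50%), in an unknown direction. Section E's denial of other threats conflicts with Sections II and III.

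The textual part rests on no assumption. The sizes rest on assumed inputs, apart from the 50% risk and the 10-20 index children. This should be changed because the stated aim is only partly served and the remedy is cheap. A reader might infer that the registry's yield is wrong or unusable; the documents do not support that.

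**What to change.** **Section F, add:**

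> We will report percent positive by degree of relationship. As descriptive counts, we will report uptake: relatives tested after the index child's positive result, divided by living first- and second-degree biological relatives aged 6 months or older on the family tree and not tested before that result. More distant relatives tested are listed separately. Relatives tested before the index child's result are excluded from both parts of the uptake fraction, reported separately, and not counted as newly identified. Relatives tested elsewhere after it count as tested. Newly identified carriers per index child will be reported over all positive index children, including those with no relative tested. If no tree exists for a family with no enrolled relative, the number of such families is reported and uptake is labelled as applying only to families with a tree.

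The denominator has to be defined because the protocol speaks variously of immediate, extended and any biological relatives.

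**Section E:** replace the denial with a statement that relatives are self-selected and reached through the parent or guardian. Label the yield *positivity among self-selected tested relatives*.

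**Optional, subject to IRB agreement:** obtain a minimal list of relatives (relationship, side, living status) from each index child's parent or guardian, so that families with nobody enrolled are covered. This goes beyond wording. It records data on people who have not consented, and where nobody enrolls it comes from a parent who is not a registry participant.

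**Cost:** some work to tabulate the trees, duplicate listings to resolve when several respondents name the same relative, and a less favourable statement on generalizability.
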